5.1 Inclusion Criteria

1. Males and females 18 years or older
2. Patient has already been admitted to ICU
3. Patient requires enteral feeding
4. Patients receiving PPI therapy
5. Informed consent by independent physician and next of kin
6. ICU ventilated patients

5.2 Exclusion Criteria

1. Patients with anomalies or diseases of the esophagus and or stomach.
2. Patients with known sensitivities or allergies to any of the feeding tube materials
3. Inability to place patient in semi-Fowler's position.
4. Any clinically significant abnormality upon physical examination which may, in the opinion of the investigator, pose difficulty in inserting the feeding tube (e.g. cervical spine disorder)
5. Pregnancy
6. Recent abdominal surgery (less than 30 days)

5.3 Duration of Study

Each patient may be enrolled in the study for a duration of 2.3 days (56 hrs.±2) up to 7 days (168 hrs.±2). No follow-up will be conducted for this study. Overall study duration is estimated to be 3 months (depending on enrollment rate).

6 Study Treatment

6.1 Type of Study

This is an open, prospective, single arm study in which the investigational device will be tested in real-life settings on patients admitted to the ICU who require enteral feeding.

6.2 Study Design

Due to the sensitive nature of potential study subjects (e.g., unconscious, critically ill, etc.), independent physician and next of kin must sign informed consent prior to initiating any study related activities.

6.2.1 Screening

All patients already admitted into the ICU who require enteral feeding may be screened for potential enrollment into the study. Patients may be included only if they meet the inclusion/exclusion criteria and informed consent has been obtained by independent physician and next of kin.

History and physical examination will be performed in order to assess subject inclusion eligibility. For women of childbearing age, a urine (or blood) pregnancy test will be performed.

The following information will be recorded for each patient found eligible to participate in the study:

- Medical history (including concomitant medications)- detailed in the CRF.
- Physical examination

6.2.2 Treatment

Following the screening procedure staff will utilize the smART System to provide enteral feeding to the patient. Feeding tube insertion and commencement of feeding should be done per patients' need and per local hospital procedures.

6.2.3 Study Specific Procedures:

- Videotaping of subject

Following the completion of the informed consent procedure and prior to feeding tube placement, a video recording of the patient will commence. The camera will be placed across from the patient focusing on the facial area and will allow recording of any movement of the tube for later comparison with the data logs recorded by the smART console. All recorded data must be attached to the CRF and serves as an integral part of the analyzable data for the study.

Specific video procedures will be supplied to the site as part of the study MOP binder.

- Initial Tube Placement:

Vital signs should be noted within 10 minutes of feeding tube insertion.

Study staff should follow the device instructions for use and specific instructions provided by the console during initial tube placement. Time of tube placement is recorded by the console.

Once initial placement is confirmed by the system, verification of correct placement should be performed by abdominal X-ray (gold standard). Note: X-ray should be performed as needed and according to hospital procedures. Once placement confirmation is obtained via x-ray, staff should use a permanent marker to indicate the edge of the nostril on the feeding tube (this mark will enable the staff to verify malpositioning warnings if they occur during on-going use).

- **Ongoing Use**

If system alerts of tube displacement during ongoing use, staff should record the event and verify based on the tube marking if malpositioning occurred and document the event. The need for tube reinsertion/repositioning should be evaluated and performed as needed.

When a reflux episode is detected by the system, the following will be initiated:

1. feeding stops
2. feeding tube balloon will automatically be inflated by the system
3. an alert will sound
4. The Y-piece block opens allowing for feeding system decompression initiating free flow of gastric content into the collection bag. The system will automatically record data relevant to reflux episodes and store it.

- **Feeding Information**

Patient information will be recorded from hospital source at the end of the study for each patient. The information will include feeding times, food amounts and types, medications provided, patient positioning, GRV times and amounts.

- **Gastric Residual Volume (GRV)**

Local site procedure for GRV should be followed as needed and according to hospital procedures. Every occurrence of GRV is supposed to be recorded by the medical staff in hospital sources (according to hospital standards).

- **Patient Positioning**

Every occurrence of patient re-positioning is supposed to be recorded by the medical staff in hospital sources. This information will later be correlated to the occurrence of reflux as recorded by the system.

SUBJECT: Functionality and Accuracy of the smART System in Real-Life ICU Settings

Number: CLT3_SY_P001

Revision 08

Page 20 of 38

- **X-Ray imaging**

Local site procedure for X-ray should be followed as needed and according to hospital procedures. Each time a thorax x-ray image is taken (as part of the patient care). Once feeding tube initial positioning is performed, X-Ray should be taken as part of the usual gold-standard care. A copy of the X-ray should be documented as part of the study CRFs/Forms.

- **Patient general clinical information**

In addition to the CRF's, patient clinical information will be collected directly from the hospital's electronic medical record by the hospital's IT department and provided to the sponsor. The clinical information may include a summary and daily reports and diagnosis, vital signs, imaging data, medications and laboratory reports, breathing and respiratory support parameters, physicians and nurses' notes and medical orders, etc.

The collected information will include valid data from 48 hours prior to feeding tube insertion up until 24 hours after the end of the study.

This information will allow for the analysis of the secondary endpoint dealing with the correlation between patient clinical information and the occurrence of reflux and sensors data.

The data may be collected at various time intervals during the study or at the end of the study once all patients have completed the study.

- **Removal of feeding tube**

Every smART feeding tube removal should be documented in the CRF and the relevant device information (i.e., serial number) should be recorded. If a smART tube is replaced by a different smART tube, the reason for replacement should be documented and the serial number of the new device being used should be recorded.

- **Endoscopy/esophageal imaging**

One third of the study population will undergo endoscopy to evaluate potential trauma to the esophagus as a result of balloon inflation.

Endoscopy will be indicated for those patients who:

- Have been enrolled in the study for a duration of more than 5 days;

Or,

- Had noticeable blood residue on the feeding tube following tube removal.

PATIENT SAFETY THROUGH TECHNOLOGY

Date issued:
05 Dec2018

SUBJECT: Functionality and Accuracy of the smART System in Real-Life ICU Settings

Number: CLT3_SY_P001

Revision 08

Page 21 of 38

If by the time patient number 13 is enrolled, no endoscopies have been performed, the remaining 7 patients will undergo endoscopy for local evaluation of trauma in the area of the esophagus where the balloon is inflated.

Every effort will be made to obtain at least 7 patients with endoscopic assessment.

Procedure - Following tube removal (within 5 hrs.) patients eligible for endoscopy (based on the above definition) shall undergo an endoscopic procedure to evaluate the balloon inflation site. Specifically, any noticeable trauma to the esophagus shall be recorded in the relevant CRF pages (e.g., adverse event form).

- Aspiration of gastric contents recording

Local site procedure for tracheal suction should be followed as needed and according to hospital procedures. Once every eight hours a sample of at least 2 cc should be instilled in a LUKI trap. The sample should be appropriately labeled and recorded by the medical staff in the bed side CRF log (Pepsin Test). The sample should be kept frozen until transportation to the lab.

- Used/Unused Devices

Used devices will be returned back to the bag in which they were provided in by the sponsor. All the bags will be collected by the sponsor, and accountability logs will be updated accordingly.

All unused devices and study materials will be collected by the sponsor at the end of the study.

- Staff Questionnaires:

At the end of the study, staff will be required to complete a usability questionnaire assessing the ease of use and functionality of the device (refer to Appendix 2).

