4.1 Primary Endpoints

Functionality

- the system is able to accurately guide the user to ensure correct initial placement (verified by X-ray)
- the system is able to detect tube movement/displacement during ongoing use (verified by markings on the tube)
- the system automatically stops feeding when tube displacement is detected
- the system automatically stops feeding when reflux is detected
- the system automatically inflates the balloon when a reflux episode is detected

Safety

- occurrence of device related adverse events

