6.2.12 Replacement of Subjects

All subjects that participate in the study for a duration of 2.3 days (56 hrs.±2) up to 7 days (168 hrs. ±2), at termination will be considered as complete. In case of premature withdrawal of subjects from the study (i.e., withdrew prior to participation of 56 hrs.±2), additional subjects may be enrolled to reach the target number following a discussion between the Principal Investigator and the Sponsor. New subjects will undergo the same procedures and assessments as specified in the protocol.

A patient will be considered officially enrolled in the study once signing ICF obtained.

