6.2.14 Subject Withdrawal or Discontinuation

Each subject (or delegate) will be informed of his/her right to withdraw from the study at any time and for any reason.

The Investigator may withdraw a subject from the study at any time if he considers that remaining in the study compromises the subject's health.

Additional criteria for withdrawal:

- The insertion of the feeding tube has failed after **2** attempts in each nostril

The reasons for any subject withdrawal will be recorded on the study completion form of the CRF. The investigator will inform the Sponsor in writing of the subject's early withdrawal for any reason.

If withdrawal is caused by an adverse event that the investigator considers may be related to the device, it will be reported to the IRB and to the Sponsor.

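### Does the lack of a scoring rule for failed insertions and unread tubes undermine the X-ray-verified placement endpoint?

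*Combined protocol and SAP*

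**What the plan says.** Section 4.1 lists as the first functionality endpoint that "the system is able to accurately guide the user to ensure correct initial placement (verified by X-ray"). It gives no denominator, unit of analysis or target rate.

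Section 6.2.3 deals with the film twice:
- Under Initial Tube Placement: "Once initial placement is confirmed by the system, verification of correct placement should be performed by abdominal X-ray (gold standard"), followed by "Note: X-ray should be performed as needed and according to hospital procedures". The nostril mark is put on the tube after X-ray confirmation.
- Under X-Ray imaging: "Local site procedure for X-ray should be followed as needed and according to hospital procedures", and then "Once feeding tube initial positioning is performed, X-Ray should be taken as part of the usual gold-standard care". A copy of the film goes into the study forms.

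Section 6.2.14 adds a withdrawal criterion: "The insertion of the feeding tube has failed after" two attempts in each nostril. The reason for any withdrawal is recorded in the CRF. Section 6.2.12 covers early leavers ("withdrew prior to participation of 56 hrs.±2), additional subjects may be enrolled to reach the target number") and makes no exception for insertion failure. It also fixes the point of entry: "A patient will be considered officially enrolled in the study once signing ICF obtained".

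Section 9.1 calls the evaluation descriptive and sets 20 subjects. Section 9.2 promises both intention-to-treat and per-protocol analyses, with categorical results given as frequencies and percentages. It defines neither set and names neither as primary.

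**The concern.** Read in sequence, these rules appear to filter the endpoint. If the film is taken only after the system has confirmed placement, the readings come from tubes the device already believes are right. A patient in whom the tube could not be passed leaves the study without a reading and may be replaced by someone in whom it could. If some confirmed tubes also go without a film, the reported percentage rests on a favourable subset.

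The choice of how to score the remaining subjects would then be made with the data in hand. For a small device study whose main product is a percentage, a reader could take a figure near 100% as success per patient attempted when it is really accuracy among confirmed and X-rayed tubes.

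**Working it through.** **Plan's own figure.** The only figure to reproduce is N = 20. Section 9.1 gives no target rate, precision, alpha or power, so it cannot be re-derived, and nothing below depends on its being right or wrong.

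**Step 1: who can lack a reading.** The Initial Tube Placement paragraph ties the film to system confirmation. The X-Ray imaging paragraph ties it to initial positioning, with no mention of confirmation. A tube that is positioned but never confirmed can therefore be X-rayed. The one case that clearly yields no film is an insertion abandoned under 6.2.14. Confirmed tubes with no film are possible under the as-needed wording. Three things in 6.2.3 make them less likely: the film is described as usual care, a copy is kept in the study forms, and the nostril mark follows the film. That mark is the reference for the second primary endpoint.

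**Step 2: which set holds them.** Enrolment is at consent (6.2.12), so a failed insertion occurs in an enrolled subject and belongs to intention to treat. Replacement adds subjects and removes none. Reaching a withdrawal criterion is not a deviation, so the clause in Section 12 that allows deviating subjects to be left out of analysis does not cover it.

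**Step 3: size.** The documents give no failure rate or missing-film rate, so the counts below are assumptions. Let f be the number of failed insertions, with every other tube read and correct.

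- Without replacement: X-rayed rate = (20 − f)/(20 − f); attempted rate = (20 − f)/20; gap = f/20.
- With replacement up to 20 X-rayed subjects: X-rayed rate = 20/20; attempted rate = 20/(20 + f); gap = f/(20 + f).
- Exact (Clopper-Pearson) 95% limits for x of n: lower = Beta quantile 0.025 with parameters (x, n − x + 1); upper = Beta quantile 0.975 with parameters (x + 1, n − x). When x = n, the lower limit is 0.025^(1/n) and the upper is 1.

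| f | X-rayed, not replaced | Attempted, not replaced | Gap (points) | Attempted, replaced | Gap (points) |
|---|---|---|---|---|---|
| 0 | 20/20 = 100% (83.2-100) | 20/20 = 100% (83.2-100) | 0 | 20/20 = 100% (83.2-100) | 0 |
| 1 | 19/19 = 100% (82.4-100) | 19/20 = 95.0% (75.1-99.9) | 5 | 20/21 = 95.2% (76.2-99.9) | 4.8 |
| 2 | 18/18 = 100% (81.5-100) | 18/20 = 90.0% (68.3-98.8) | 10 | 20/22 = 90.9% (70.8-98.9) | 9.1 |
| 3 | 17/17 = 100% (80.5-100) | 17/20 = 85.0% (62.1-96.8) | 15 | 20/23 = 87.0% (66.4-97.2) | 13.0 |

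With replacement, the X-rayed rate is 20/20 = 100% (83.2-100) in every row.

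Adding two confirmed tubes without a film to two failures among 20 attempted gives 16/16 = 100% (79.4-100) among those X-rayed. Per attempt it is 16/20 = 80.0% (56.3-94.3) if the unread tubes are not counted as correct, and 18/20 = 90.0% (68.3-98.8) if both were correct.

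**Step 4: what the gap changes.** There is no hypothesis test and no threshold for this endpoint, so no pass or fail conclusion turns on which row occurs. Section 9.2 promises frequencies as well as percentages, so numerator and denominator will be on the page, and 18/18 beside 20 enrolled shows the two missing subjects.

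**The case for a change.** The best case for a change is that being in the intention-to-treat set does not give a subject an outcome. Someone with no film can be scored as a failure, treated as missing or left out, and the percentage differs each time. In a study with no test the percentage is the result, so its denominator deserves to be fixed in advance. The endpoint also speaks of guiding the user, and a tube that never reached the stomach bears on that. The remedy would cost a few sentences.

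Much of this stands as fact. The scoring rule is absent, neither analysis set is defined or ranked, the replacement rule has no exception for insertion failure, and the X-ray wording is loose.

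The inference is weaker. No section plans a rate restricted to X-rayed subjects, so the overstatement needs both failures to occur and an unfavourable way of filling the gap. The restricted rate is itself a valid accuracy measure and matches the first objective in Section 3, which concerns the system's ability to detect correct placement. Scoring every failed insertion as a failure of guidance is a choice too: inability to pass a tube may be anatomical. Exclusion criterion 4 already removes patients in whom the investigator expects difficulty, which should keep such cases few. Per-attempt success is a reasonable estimand, but the endpoint's wording does not single it out.

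**Conclusion.** No change to the plan is needed. The gap is real but narrow: it mainly concerns insertions abandoned under 6.2.14. It is worth nothing if none occur and every tube is read, and about 5 points per failed insertion at 20 subjects. All non-zero figures rest on assumed counts, because the documents supply none.

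The plan already retains the affected subjects in a reported set, records why they left, and presents counts with percentages. An analyst would ordinarily give the correct rate among tubes read beside the rate among subjects attempted, and list failed insertions and tubes without a film. Nothing in the plan stands in the way of that. With a descriptive purpose and no threshold, declaring one set primary would alter no decision. The as-needed and should-be-taken phrases in 6.2.3 are loosely joined; I take no view on when a film should be obtained, and the number of tubes without one will show from the copies kept with the study forms.

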Insertion of nasal feeding tubes can be performed blindly at bedside or with fluoroscopic or endoscopic guidance into the stomach.

SUBJECT: Functionality and Accuracy of the smART System in Real-Life ICU Settings

Number: CLT3_SY_P001

Revision 08

Page 9 of 38

[figure not shown]
Although generally safe and effective, they are usually inserted blindly at the bedside and there is a wide spectrum of known complications associated with feeding tube placement. The most common serious complication is misplacement of the feeding tube into the bronchial tree with resulting pneumonitis, pneumonia, and/or pneumothorax if not recognized. This is reported to occur in **2.4%–3.2% of nasogastric insertions** (James L, et al. 2012).

Recent studies have suggested that 0.1 to 0.3% of all patients who were blindly placed of their feeding tubes die as a result of bronchopulmonary injury from misplaced tubes (Sorokin R et al. 2006) (Aguilar-Nascimento JE, et al. 2007).

It is estimated that approximately **1.2 million feeding tubes are placed each year in the United States alone** (Koopmann MC et al. 2011). If these tubes were placed blindly this would translate to **3,600 to 8,400 pulmonary injuries, and 1,200 to 3,600 deaths in the United States each year**. Hundreds of thousands of patients require NG tubes each year in the UK. Although the precise number is not known, the NHS Purchasing and Supply Agency (PASA) which distributes NG tubes has estimated that between 750,000 to 1,000,000 tubes are used each year within the NHS1. In addition to those used within the NHS, private hospitals, hospices and nursing homes are expected to greatly increase the number of tubes used annually. Currently, X-ray is the gold standard method for detecting the position of nasogastric tubes (Hedberg et al, 2005). However, staff does not use it routinely due to cost, risk of radiation exposure, and delay in feeding (National Patient Safety Agency, 2011; 2005). In addition, the National Patient Safety Agency (NPSA) has drawn attention in 2011 to the risk of misinterpretation of X-rays used to confirm the position of a nasogastric tube. Positioning complications are also occurring throughout the duration of the use of the tube. Movement of the distal tip of the feeding tube occurs even when the NG tube is taped in place. This is most likely to occur with soft, small-bore NG tubes. Malpositioning of the indwelling tube may result in injury or aspiration.

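### No reference reading is protected from the console's result, so the placement and displacement accuracy endpoints are at risk of upward bias of unknown size

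*Combined protocol and SAP*

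**What the plan says.** Section 4.1 of the combined protocol and SAP sets two functionality endpoints against an outside reference: initial placement against X-ray, and displacement during use against marks on the tube. Section 6.2.3 describes three sources of reference data.

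- **X-ray.** The console decides first: "Once initial placement is confirmed by the system, verification of correct placement should be performed by abdominal X-ray (gold standard"). Under the X-ray imaging item, "X-Ray should be taken as part of the usual gold-standard care", and a copy is filed with the study forms. The section names no reader, gives no reading criteria, and does not say what the reader is told.
- **Tube mark.** "If system alerts of tube displacement during ongoing use, staff should record the event and verify based on the tube marking if malpositioning occurred". The mark's stated purpose is that "this mark will enable the staff to verify malpositioning warnings if they occur during on-going use". No distance is given that counts as movement.
- **Video.** Recording starts before the tube is placed and permits "recording of any movement of the tube for later comparison with the data logs recorded by the smART console". The recordings count as analysable study data, although Section 4.1 does not name video as a reference. Detailed video procedures are left to the MOP binder, which is not among the documents.

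On design, Section 6.1 says: "This is an open, prospective, single arm study in which the investigational device will be tested in real-life settings". No section masks any of these readings. Section 9.1 plans 20 subjects and a descriptive analysis, with no target accuracy.

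**The concern.** An accuracy rate means what it says only if the reference is read independently of the device under test. A reader who knows the device's answer tends to settle doubtful cases in its favour, and the rate then partly measures agreement with a known answer. The usual safeguard is to withhold the device result from the reader, or to replace judgement with a measurement. The plan describes neither.

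What is at stake is the credibility of two of the primary functionality results. No performance target is set, so the raw observed rates will be read as the study's finding, and nothing else in the design would reveal a lenient reading.

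**Working it through.** **Step 1. What each reader knows (Section 6.2.3).**

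- Tube mark: the alert triggers the check, so the reader knows the verdict. The instruction is to "verify based on the tube marking if malpositioning occurred and document the event". With no distance defined, the outcome is a judgement.
- X-ray: the film follows console confirmation. Reader, request wording and criteria are unstated, so knowledge of the verdict is possible but not shown.
- Video: the recording itself does not depend on alerts. Reader and order of reading are unstated in the protocol, and the MOP may cover them.

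**Step 2. Sensitivity to one film.** Input: n = 20 (Section 9.1), taking one film per subject. The plan gives no accuracy figure or precision target to reproduce. Exact (Clopper-Pearson) 95% limits:

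- 20/20: the lower limit solves p^20 = 0.025, so p = 0.025^(1/20) = 0.832. Interval 83.2% to 100%.
- 19/20: the lower limit solves p^20 + 20 p^19 (1 − p) = 0.025, so p = 0.751. The upper limit solves 1 − p^20 = 0.025, so p = 0.975^(1/20) = 0.999. Interval 75.1% to 99.9%.

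One reading shifts the estimate by 5 points and the lower limit by 83.2 − 75.1 = 8.1 points. This does not say how likely such a misreading is. No parallel figure can be given for displacement, because the number of alerts is unknown.

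**Step 3. Illustration of the mechanism.** Let p be true agreement and f the share of true disagreements that an unmasked reader calls agreement. Observed agreement = p + (1 − p)f. Both p and f are assumptions; the documents give neither.

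- p = 80%: observed 82%, 85%, 90% for f = 0.10, 0.25, 0.50.
- p = 90%: observed 91%, 92.5%, 95%.
- p = 95%: observed 95.5%, 96.25%, 97.5%.

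Over these assumptions the inflation is 0.5 to 10 points. At p = 90%, the chance of a perfect 20/20 is 0.90^20 = 12.2% with f = 0, 0.925^20 = 21.0% with f = 0.25, and 0.95^20 = 35.8% with f = 0.50. If f = 0, there is no inflation.

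The direction is likely but not guaranteed. If readers also wrongly call a share e of true agreements a disagreement, the two errors cancel at e = (1 − p)f/p. For p = 90% and f = 0.25 that is 0.10 × 0.25 / 0.90 = 2.8%.

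**Step 4. What the published misplacement rate adds.** Section 1.1 quotes 2.4% to 3.2% bronchial misplacement. For 20 insertions this gives 20 × 0.024 = 0.48 to 20 × 0.032 = 0.64 expected events, and a chance of none of 0.976^20 = 61.5% to 0.968^20 = 52.2%. This shows that few events are expected in 20 subjects. It would be equally true with masked readers, so it is no measure of the bias.

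**The case against.** The strongest reply is that unmasked reading is shown for only one reference. A reader might infer that the X-ray, mark and video readers all know the console result and that the rates are therefore biased upward. The documents do not support that. The film is routine hospital care, and a console-then-film sequence does not show that whoever reads it has been told the result. The video runs regardless of alerts, and its rules are in a manual not available here, so a missing reading order is not established. Upward bias is a reasonable expectation, not a finding.

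Two further inferences should be resisted. Section 1.1 mentions "the risk of misinterpretation of X-rays used to confirm the position of a nasogastric tube", but that is a general risk and not evidence that readers follow a device's answer. Nor does the protocol say that the mark is recorded as a yes/no item; the CRF is not available.

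It can also be said that this is an open, descriptive field study, that bedside staff cannot be masked from an alarm, and that filed films and recordings would allow a later masked reading. All of this is fair, and it limits the point. It does not remove it: a later re-reading is possible but not planned, and the mark judgement cannot be repeated afterwards. Followed as written, Section 6.2.3 yields an unquantified judgement by someone who knows the verdict, on the reference that Section 4.1 names for displacement.

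**Conclusion.** The point holds as a risk. No reference reading is protected from the console's result, and both accuracy endpoints are exposed to upward bias of unknown size. Knowledge of the verdict is certain for the tube mark, possible and not excluded for the X-ray, and not excluded for the video pending a check of the MOP. The 5-point shift from 19/20 to 20/20 shows only how much one film counts at this sample size; the 0.5 to 10 point range rests entirely on assumed values of p and f.

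The study can run without the change, but its two accuracy endpoints would be open to an avoidable challenge, so the change should be made. A separate problem remains: the mark is checked only after an alert, so displacements that the console misses are not seen by that reference. Masking does not cure this.

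**What to change.** Change Section 6.2.3 and the video procedure, after checking whether the MOP already sets a reading order.

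1. **Tube mark.** At each displacement alert, record the distance in cm and the direction from the mark to the nostril. In the analysis, classify displacement against a distance that the sponsor fixes beforehand. This makes the reading more objective but does not mask it.
2. **Video.** Read each recording into a time-stamped list of tube movements, and lock the list before the console log is opened. The same person can do both. Use the list as the alert-independent check on displacement. It can show movement of the visible part of the tube only.
3. **X-ray.** Take the placement endpoint from the tip location in the routine radiology report, requested without stating the console result. Bedside use of the film is unchanged.

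The cost is protocol wording, one added CRF field, and a fixed reading order that must be kept. The hospital may need to agree to the wording of the X-ray request. Sample size does not change, and no reader, film or patient is added. The mark measurement must be in place before data are collected, since it cannot be recovered later.
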